**Intervention Groups and Duration:****Part 1: Single Dose Escalation and Food Effect in Healthy Adult Participants**

Part 1 will consist of a maximum of four periods in a cross-over design conducted in two separate cohorts of eight healthy participants. Each of these two cohorts may participate in a maximum of four periods and will receive three doses (escalations or reductions) of GSK3882347 and a potential assessment of food effect. The food effect evaluation will be conducted in only one of the cohorts which will be selected based on the observed human pharmacokinetics. The planned starting GSK3882347 dose in Part 1 is 50 mg administered as a single oral dose. The dose is planned to increase in subsequent cohorts to 150, 250, 500, 750, and 900 mg. In each escalating dose level, six participants will be randomized to GSK3882347 and two participants will be randomized to placebo.

Participants who meet the criteria for study entry will be assigned to a cohort and randomized to receive GSK3882347 or placebo in a 3:1 ratio before administration of study intervention on Day 1 in Part 1. As a safety precaution, cohorts 1 and 2 will be split into two sub-cohorts to allow sentinel dosing. At each dose level (Cohort 1 and 2), the first two participants will receive either GSK3882347 or placebo (one active and one placebo). Dosing of the remaining six participants (five active and one placebo) in that cohort will occur at least 24 hours later based on review of the safety data (e.g. vital signs, ECGs, clinical laboratory results and adverse events) by the Principal Investigator and sponsor Medical Monitor from all sub-cohorts of sentinel participants. Doses are planned to escalate in a sequential fashion contingent on the safety, tolerability and pharmacokinetic profile of a minimum of four participants who received active treatment in the previous cohort. Dose escalations or reductions will progress with modifications based on the clinical safety, tolerability and preliminary PK data consideration of the area under the concentration-time curve (AUC) from time zero to 24 hours after dosing (AUC[0-24]) and maximum plasma concentration (Cmax) exposures based on the no-observed-adverse-effect-level (NOAEL) from the preceding cohorts.

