### 2.3.2. Risk Assessment

Potential Risk of Clinical Significance	Summary of Data/Rationale for Risk	Mitigation Strategy
Investigational Product (IP) GSK 3882347		
Gastrointestinal toxicity (including body weight loss, decreased food consumption and dehydration)	
Dogs given <math>\geq 300</math> mg/kg/day had severe body weight loss, decreased food consumption, dehydration, emesis and abnormal feces. Dogs given 1000 mg/kg/day were euthanized early due to severity of body weight loss.
 
Pregnant rabbits given <math>\geq 300</math> mg/kg/day had severe body weight loss and decreased food consumption, which resulted in early euthanasia and 1 early death at 900 mg/kg/day.
 
These changes in dogs and rabbits resulted in early euthanasia or death at the doses stated. Nonclinical Risks – concluding sections of the Non-Clinical Assessment of Safety (NCAS) should provide key nonclinical risks associated with the IP.
	
 
• Dosing for a maximum of 7 days.
 
• Standard clinical monitoring with elicitation of clinical symptoms; physical examinations and routine safety blood haematology and chemistry tests.
 
• Monitoring for AEs.
 
• Monitoring daily fluid balance in participants.
 
• Gastrointestinal stopping criteria: Participant will continue to dose through grade 1 toxicity, interrupt dosing for grade 2 toxicity and discontinue drug for grade 3-4 toxicity (for the latter, consultation with GI experts will occur with no plan for drug restart) (see Section 7.1.1)
 
• Monitoring of stool type with the Bristol stool chart to identify changes in bowel
 

Potential Risk of Clinical Significance	Summary of Data/Rationale for Risk	Mitigation Strategy
		habit which may represent gastrointestinal toxicity.
OTHER		
COVID-19	
Participation within a hospital environment may increase risk of contracting COVID-19.
 
Exposure to other participants and staff may increase risk of exposure.
	

• Monitoring of clinical presentation of COVID-19 signs/symptoms.

• Conduct study at sites which have appropriate mitigation strategies in place.

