#### 7.1.1. Gastrointestinal Events (diarrhea or colitis)

[figure not shown]
Grade	Diarrhea	Management	Follow-up
Mild (Grade 1)  An event that is easily tolerated by the participant, causing minimal discomfort and not interfering with everyday activities	Increase of <4 stools per day over Baseline	
 
Administer antidiarrheal and symptomatic treatment as appropriate
 
Discuss participant continuation in the trial with Sponsor/Medical Monitor
 
	
Symptoms resolve to baseline within 3 days:
 
 
Provide close follow-up to evaluate for increased severity.
 
 
Symptoms ongoing > 3 days:
 
 
Consider following algorithm for Grade 2 events
 

Moderate (Grade 2)  An event that causes sufficient discomfort and interferes with normal everyday activities	Increase of 4 - 6 stools per day over Baseline	
 
Interrupt study drug(s)
 
Administer antidiarrheal and symptomatic treatment
 
Investigate etiology; consider consulting GI service
 
Discuss participant continuation in the trial with Sponsor/Medical Monitor
 
	
Symptoms resolve to ≤ Grade 1 or baseline within 7 days:
 
 
Continue follow-up and evaluate for any increased severity.
 
 
Symptoms ongoing > 7 days, blood or mucus in stool, or ulceration/bleeding on endoscopy:

Grade	Diarrhea	Management	Follow-up
			
 
Consider following algorithm for Grade 3 events
 

Severe (Grade 3-4) An event that prevents normal everyday activities	Grade 3: Increase of $\geq 7$ stools per day over Baseline; incontinence; hospitalisation indicated  Grade 4: life-threatening consequences; urgent intervention indicated	
 
Discontinue study drug(s)
 
Consult GI service
 
Discuss participant continuation in the trial with Sponsor/Medical Monitor
 
	
Symptoms ongoing:
 
 
Continue follow up of participant
 
Discuss further management with GI consultant and Sponsor/Medical Monitor
 

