### 7.1.4. Individual Stopping Criteria

- Any participant who experiences an SAE will be withdrawn from the study.
- Any participant who experiences an AE of moderate or severe intensity that is considered attributable to dosing with GSK3882347 will be withdrawn from the study.
- If a participant develops COVID-19 like symptoms during the course of the study the following actions should be taken:
  - During Part 1 (SAD portion of the study), participants who develop a high clinical index of suspicion for COVID-19 disease should be isolated and tested for COVID-19 in accordance with site procedures.
  - During Part 2 (MAD portion of the study), study treatment should be halted for any participants who develop a high clinical index of suspicion for COVID-19 disease; they should be isolated and tested for COVID-19 in accordance with site procedures.
  - In both cases, assessments should be continued as per the protocol during this period; withdrawal of participants from the study will be at the discretion of the Principal Investigator, but should first be discussed and agreed with the GSK Medical Monitor.

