## 7.3. Participant Discontinuation/Withdrawal from the Study

- A participant may withdraw from the study at any time at his/her own request or may be withdrawn at any time at the discretion of the investigator for safety, behavioural, compliance or administrative reasons. This is expected to be uncommon.
- At the time of discontinuing from the study, if possible, an early discontinuation visit should be conducted (assessments in the follow-up visit), as shown in the SoA in Section 1.3. See SoA for data to be collected at the time of study discontinuation and follow-up and for any further evaluations that need to be completed.
- The participant will be permanently discontinued both from the study intervention and from the study at that time.
- If the participant withdraws consent for disclosure of future information, the sponsor may retain and continue to use any data collected before such a withdrawal of consent.
- If a participant withdraws from the study, he/she may request destruction of any samples taken and not tested, and the investigator must document this in the site study records.

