### 10.3.3. Recording and Follow-Up of AE and SAE

AE and SAE Recording

When an AE/SAE occurs, it is the responsibility of the investigator to review all documentation (e.g., hospital progress notes, laboratory, and diagnostics reports) related to the event.

The investigator will then record all relevant AE/SAE information in the CRF.

It is not acceptable for the investigator to send photocopies of the participant's medical records to GSK in lieu of completion of the GSK /AE/SAE CRF page.

There may be instances when copies of medical records for certain cases are requested by GSK. In this case, all participant identifiers, with the exception of the participant number, will be redacted on the copies of the medical records before submission to GSK.

The investigator will attempt to establish a diagnosis of the event based on signs, symptoms, and/or other clinical information. Whenever possible, the diagnosis (not the individual signs/symptoms) will be documented as the AE/SAE.

Assessment of Intensity

The investigator will make an assessment of intensity for each AE and SAE reported during the study and assign it to 1 of the following categories:
 

Mild: An event that is easily tolerated by the participant, causing minimal discomfort and not interfering with everyday activities.

Moderate: An event that causes sufficient discomfort and interferes with normal everyday activities.

Severe: An event that prevents normal everyday activities. An AE that is assessed as severe should not be confused with an SAE. Severe is a category utilized for rating the intensity of an event; and both AE and SAE can be assessed as severe.

 
An event is defined as 'serious' when it meets at least 1 of the predefined outcomes as described in the definition of an SAE, NOT when it is rated as severe.

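### A drug-attributed Grade 2 gastrointestinal event falls under two different stopping rules (interrupt, or withdraw), and the protocol does not say which governs

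*Protocol*

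**What the plan says.** Four parts of the protocol bear on a Grade 2 GI event.

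- **2.3.2 Risk Assessment.** Under the investigational-product heading, the GI stopping criteria continue dosing through Grade 1, then "interrupt dosing for grade 2 toxicity and discontinue drug for grade 3-4 toxicity". The qualifier that follows reads "for the latter, consultation with GI experts will occur with no plan for drug restart", where the latter means Grade 3-4. The bullet refers to 7.1.1 and not to 7.1.4.
- **7.1.1 Gastrointestinal Events.** Grade 2, labelled Moderate, is defined as "An event that causes sufficient discomfort and interferes with normal everyday activities". The management column says to interrupt the drug, treat, look into the cause, and discuss with the sponsor or Medical Monitor whether the participant continues. If the event settles within 7 days, the only instruction is continued follow-up. Discontinuation of the drug appears only in the Grade 3-4 row. A Grade 2 participant is considered for that row only if symptoms exceed 7 days, there is blood or mucus in the stool, or endoscopy shows ulceration or bleeding.
- **7.1.4 Individual Stopping Criteria.** Any participant with an "AE of moderate or severe intensity that is considered attributable to dosing with GSK3882347 will be withdrawn from the study". There is no exception for GI events.
- **7.3 Participant Discontinuation/Withdrawal.** "The participant will be permanently discontinued both from the study intervention and from the study at that time".

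Appendix 3 (10.3.3) supplies the intensity scale: "Moderate: An event that causes sufficient discomfort and interferes with normal everyday activities".

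**The concern.** The same event can be read under two rules with different outcomes. The GI rule holds the drug and leaves continuation to discussion. The individual stopping rule removes the participant. Neither 2.3.2 nor 7.1.1 points to 7.1.4 or restricts interruption to events judged unrelated to the drug.

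The stakes are participant protection. GI toxicity is the only investigational-product risk in the 2.3.2 table, supported there by severe findings in dogs and rabbits, including early euthanasia and a death. Participants are healthy volunteers who, by 2.3.3, derive no medical benefit. A site managing a GI event would naturally turn to the GI section, and there it would find the less protective of the two rules.

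**Working it through.** There is no planned figure to reproduce. The check compares the texts and then bounds the exposure at issue.

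**1. Do the rules cover the same event?** The Grade 2 definition in 7.1.1 and the Moderate definition in 10.3.3 are word for word the same. A Grade 2 event considered attributable to GSK3882347 is therefore a moderate attributable adverse event, which is the trigger in 7.1.4.

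**2. Do they lead to the same action?**

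| Attributed event | 2.3.2 and 7.1.1 | 7.1.4 with 7.3 |
|---|---|---|
| Grade 2 | Interrupt; discuss continuation; follow up if resolved within 7 days | Withdraw from the study, permanently |
| Grade 3-4 | Discontinue drug; no restart planned; discuss continuation in the trial | Withdraw from the study, permanently |

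For Grade 3-4 the drug stops under both. For Grade 2 it need not. Neither 2.3.2 nor 7.1.1 expressly directs a restart. The possibility is inferred from three features: interrupt is set against discontinue, the no-restart statement is confined to Grade 3-4, and continuation is left open for discussion. If 7.1.4 already removed every attributed Grade 2 participant, the grade distinction in 2.3.2 would have no effect for attributed events, although 2.3.2 presents it as mitigation for the product's own toxicity.

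**3. How much further exposure could follow in Part 2?** Doses are given on Days 1 to 7. Assume onset after the Day d dose, at least one dose held, and resumption on Day r, with r ≥ d + 2.

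Further doses = 7 − r + 1 = 8 − r. With the earliest r = d + 2, the maximum is max(0, 6 − d).

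| Onset after dose on Day | 1 | 2 | 3 | 4 | 5 | 6 | 7 |
|---|---|---|---|---|---|---|---|
| Maximum further doses, GI rule alone | 5 | 4 | 3 | 2 | 1 | 0 | 0 |
| Further doses under 7.1.4 | 0 | 0 | 0 | 0 | 0 | 0 | 0 |

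The last day on which dosing could resume is Day 7, which is 7 − 1 = 6 days after a Day 1 onset. An event that uses the whole 7-day resolution window therefore leaves no dose to give.

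**4. And in Part 1?** Each period is a single dose, so the question is entry to later periods. The Synopsis states: "Each of these two cohorts may participate in a maximum of four periods and will receive three doses". For an event in Period p:

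- if four periods are used, 4 − p remain: 3, 2, 1, 0 for p = 1 to 4;
- if only the three planned dose periods are used, 3 − p remain: 2, 1, 0 for p = 1 to 3.

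Some of these may be placebo, because two of the eight participants receive placebo at each dose level. Planned doses rise from 50 to 900 mg, so a later active period could be at a higher dose. Under 7.1.4 the number is 0.

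**The case against.** The strongest reply is that nothing here is contradictory. No text authorises re-dosing after Grade 2. 7.1.4 is mandatory and 7.1.1 is discretionary, so both can be obeyed: interrupt at once, investigate the cause (which the Grade 2 row requires), and withdraw if the event is attributed. Interruption with possible continuation then keeps a real use for unrelated diarrhoea. Re-dosing would need both the investigator and the Medical Monitor to overlook a stopping criterion in the same part of Section 7, and Section 8 separately requires immediate safety concerns to go to the sponsor. The 7.1.1 table grades by stool count, so the overlap is in practice diarrhoea or colitis rather than every GI sign named in 2.3.2. The dose counts are ceilings.

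Much of this stands. The reconciling sequence is workable, the Medical Monitor discussion is a real safeguard, and the exposure figures are upper bounds. The gap also mainly concerns an isolated case, because two similar moderate events in two or more participants halt dosing at that level under 7.2.

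What does not stand is the claim that the sequence is already in the protocol. 7.1.1 draws no distinction by causality, and 2.3.2 offers interruption as the response to toxicity of the product itself, which is the attributable case. Where the protocol means to bar restart it says so, as 7.1.2.1 does for liver events. For a stopping rule in a first-in-human study, the order of actions should not be left to inference.

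**Conclusion.** The concern holds. For a drug-attributed Grade 2 GI event, the GI rule and the individual stopping rule prescribe different actions, and no precedence is stated. The size, per affected participant, is at most 5 further doses in Part 2 and at most 3 later periods in Part 1, against 0 under 7.1.4. The Part 2 ceiling assumes onset after the Day 1 dose, one dose held and dosing resumed on Day 3. The Part 1 ceiling assumes an event in Period 1 and use of all four periods. Both assume that the site and Medical Monitor act on the GI rule without applying 7.1.4. The protocol gives no event rate, so no expected frequency is offered. The reading of 7.3 as covering 7.1.4 withdrawals is fair but not essential, since withdrawal from the study already excludes further dosing. This should be corrected. It does not call the design into question.

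**What to change.** State in the 2.3.2 bullet and in the Grade 2 row of 7.1.1 that 7.1.4 governs attributed events. Suitable wording: interrupt dosing at onset; if the event is considered attributable to GSK3882347, give no further dose and withdraw the participant under 7.1.4; interruption with discussion of continuation applies only to events judged not attributable. Add the same cross-reference to the Grade 3-4 row, which also leaves continuation in the trial to discussion.

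The cost is one sentence in 2.3.2, one in the Grade 2 row and one cross-reference in the Grade 3-4 row, made at the next amendment. Sample size, assessments and dosing are unchanged, and the Synopsis and 9.2 already allow withdrawn participants to be replaced.

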### 2.3.3. Benefit Assessment

This is a study in healthy participants; no medical benefit will be derived by volunteers' participation. However, participants in this study may be contributing to the development of new therapies in an area of unmet need.

### 2.3.4. Overall Benefit: Risk Conclusion

Given the preclinical profile of GSK3882347, measures taken (careful selection of the participants and the extent of safety monitoring incorporated into the study) and the planned clinical procedures and evaluations in this study, the potential risks to participants receiving GSK3882347 are low, evaluable, and manageable.

## 3. OBJECTIVES AND ENDPOINTS

Objectives	Endpoints
Primary	
 
To evaluate the safety and tolerability of GSK3882347 following oral administration of single and repeat doses in healthy adult participants
 
To evaluate the pharmacokinetics of GSK3882347 in plasma and urine following oral administration of single and repeat doses in healthy adult participants
 

	
 
Occurrence of adverse events (AEs) and treatment related AEs
 
Occurrence of clinically significant changes in vital signs, laboratory parameters, and 12-lead electrocardiogram (ECG) findings
 
Single dose (plasma): AUC(0-24), AUC(0-t), AUC(0-inf), Cmax, C24h, tmax, tlag and t1/2 of GSK3882347, as data permit
 
Repeat dose (plasma): AUC(0-tau), Cmax, tmax and Ctau of GSK3882347, as data permit
 
Urine concentration at 22-24h collection time-point
 
Amount excreted in urine (Ae) of unchanged GSK3882347, fraction of the dose excreted in urine (fe) and renal clearance (CLr), as data permit
 

Secondary	
 
To further evaluate the pharmacokinetics of GSK3882347 in plasma
 
Single dose(plasma): AUC(0-12), C12h, CL/F, Vd/F and MRT of GSK3882347, as data permit
 

Objectives	Endpoints

 
• To examine dose proportionality of GSK3882347 following oral administration of single and repeat doses in healthy adult participants
 
• To evaluate the extent of accumulation, time invariance, and achievement of steady-state of GSK3882347 following oral administration of single and repeat doses in healthy adult participants
 
	
 
• Repeat dose (plasma): AUC(0-12) and C12h of GSK3882347, as data permit
 
• AUC(0-inf) and Cmax for single dose and AUC(0-tau) and Cmax for repeat dose, as data permit
 
• Ro (accumulation ratio) using AUC(0-tau) for repeat dose, as data permit
 
• Time invariance using AUC(0-tau) (repeat dose) and AUC(0-inf) (single dose)
 
• Achievement of steady-state (Ctau collected on multiple days)
 


 
• To evaluate the effect of food on pharmacokinetics of GSK3882347 following oral administration of single dose in healthy adult participants
 
	
 
• AUC(0-24), AUC(0-t), AUC(0-inf), C24h, Cmax, tmax and tlag, as data permit
 

Exploratory 
 
• To assess ECG effects of GSK3882347, including concentration-QTc analysis, following single and repeat doses in healthy adult participants
 
	
 
• Change-from-baseline QTc (<math>\Delta</math>QTcF)
 
• Change-from-baseline heart rate, PR and QRS interval (<math>\Delta</math>HR, <math>\Delta</math>PR and <math>\Delta</math>QRS)
 
• Placebo-corrected <math>\Delta</math>QTcF, <math>\Delta</math>HR, <math>\Delta</math>PR and <math>\Delta</math>QRS
 
• Treatment emergent T-wave abnormalities and presence of U-waves
 
• Categorical outlier analysis for HR, QTcF, PR and QRS
 

Objectives	Endpoints

 
To investigate the plasma and urine metabolic pathways of GSK3882347 in healthy participants
 
	
 
Characterization of the plasma and urinary metabolites of GSK3882347, estimation of the percentage dose eliminated in urine, where possible
 

 
To characterize the effect of GSK3882347 on intestinal microbiota following single and repeat doses in healthy adult participants
 
	
 
Change in intestinal microbiome over time
 

 
To assess potential effect of repeat doses of GSK3882347 on Cytochrome P450 3A4 (CYP3A4) enzyme activity in Part 2
 
	
 
Plasma 4β-hydroxycholesterol to cholesterol ratio at pre-treatment and following repeat dosing of GSK3882347
 

Note: The exploratory endpoints may be analyzed as GSK3882347 clinical development continues.

## 4. STUDY DESIGN

### 4.1. Overall Design

This is a two-part phase I, FTIH, randomized, double-blind, single-center, placebo-controlled, dose-escalation study to determine the safety, tolerability and pharmacokinetics of GSK3882347 following oral administration of single (Part 1) and repeat doses (Part 2) in healthy adult men and WONCBP. Part 1 will consist of two cohorts with a maximum of four-period cross-over. The food effect evaluation will be conducted in the last period (Period 4) in only one of the cohorts based on the observed human pharmacokinetics.

During Parts 1 and 2, participants who meet the criteria for study entry will be assigned to the current dose level and randomized to receive GSK3882347 or placebo before administration of study intervention on Day 1.

Dose escalation will be conducted only if it is supported by safety, tolerability and pharmacokinetic results from the preceding dose level(s). This is the first administration of GSK3882347 in humans; therefore, preliminary safety, tolerability and pharmacokinetic results will be reviewed internally at GSK in conjunction with the study site and study design adjustments may be made based on emerging data from each dose cohort. The repeat dose escalation component (Part 2) of this study will be initiated once safety at an exposure that exceeds the daily exposure predicted at steady state for the Part 2 planned starting dose of 50 mg has been demonstrated in Part 1. This is predicted to occur at the 250 mg single dose. The point at which Part 2 is initiated can be modified based on the emerging safety, tolerability and pharmacokinetic data from Part 1.

In Part 1, participants will remain in the clinical unit from admission on Day-1 until all scheduled safety and pharmacokinetic assessments have been completed for that dose (approximately 5 days) for each period. The duration of study participation will be approximately 3 months (~30 days screening, 5 days in-house assessment for the

completion of a maximum of the four periods, 2 weeks between each dose escalation and ~14-day follow-up period) for completion of up to four periods. Part 1 will consist of two cohorts with up to a four-period cross-over. The food effect evaluation will be conducted in last period (Period 4) in only one of the cohorts based on the observed human pharmacokinetics.

In Part 2, participants will remain in the clinical unit from admission on Day-1 until after all scheduled safety and pharmacokinetic assessments have been completed (approximately 5 days post the last dose or 5 half-lives, whichever is longer based on the emerging data from Part 1). The duration of study participation will be up to approximately 8 weeks (~30 days screening, up to 12 days in-house assessment period, and ~14-days follow-up period).

Study schematic is provided in [Figure 1](#).

